13.1.4 Post-Workshop Sample Collection

Immediately after workshops, participants will be offered same-day opportunity to engage in cervical cancer screening either through clinician collection (if in the control) or self-collection (if in the intervention group). Participants who do not desire screening through the program will be encouraged to attend cervical cancer screening with their local health department or provider.

Pregnant women will be excluded from this study if they are known to be pregnant at the time of screening, although additional measures will be taken prior to sample collection for women unaware of pregnancy status. All participants will be asked the date of their last menstrual period (LMP). Participants will be requested to provide a urine sample for on-site urine pregnancy testing if more than six weeks from LMP unless post-menopausal or meeting criteria of relative certainty a woman is not pregnant. CDC 2016 Selective Practice Recommendations for reasonable certainty states, a health care provider can be reasonably certain that women is not pregnant if she has no symptoms or signs of pregnancy and meets any one of the following criteria:

- is ≤7 days after the start of normal menses
- has not had sexual intercourse since the start of last normal menses
- has been correctly and consistently using a reliable method of contraception
- is ≤7 days after spontaneous or induced abortion
- is within 4 weeks postpartum
- is fully or nearly fully breastfeeding (exclusively breastfeeding or the vast majority [≥85%] of feeds are breastfeeds), amenorrheic, and <6 months postpartum¹⁴

Results of the urine pregnancy test will be provided immediately to the participant and if positive, excluded from the remaining of the study although still counted as a participant. Due the possibility that participants who are pregnant and included in the study (educational workshops only, will not be included in either screening method—clinician-collected or self-collection). For risks involved with the educational workshop portion of the study:

- The research involves no more than minimal risk to pregnant women and fetuses.
- The research holds prospect of direct benefit to the pregnant women, the prospect of direct benefit both to the pregnant woman and the fetus, or no prospect of benefit for the woman nor the fetus.
- The educational workshops on cervical cancer provided potential benefit by prevention of cervical cancer in the woman and reduction of morbidity and mortality which may have subsequent benefit to the fetus.

Physicians from UW- Madison will be made available to assist in either group with CHWs as approved translators to guide collection.

13.1.4.1 Self-Swab Vaginal Samples

Participants will be provided a private area of their choice (exam room or bathroom) to self-collect vaginal samples. Device which will be used is the Evalyn® Brush (Rovers Medical Devices, Netherlands) which has FDA and CLIA approval. The device is self-directed by the participant and will include translated instructions in Hmong, Karen, and Burmese and Karen. Instructions will also be provided to all participants orally. The device is neither implanted nor creates a potential for serious risk to the health, safety, or welfare of the subject. A picture of the device and instructions for self-collected provided by the manufacturer are included in Appendix B. There are no known potential serious risks to the health, safety, or welfare of the subject. [name] will be available onsite to answer any questions or concerns participants have during the self-collection process.

13.1.4.2 Clinician-Collected Cervical Samples

The provider ([name]) will obtain a sample in the normal standard fashion using speculum to collect cervical samples. Samples will be collected in ThinPrep vials for Pap smear and HPV testing.

Self-collected samples will be packaged for disposition and transported to the Penn State Health Medical Group Laboratory for processing and evaluation. Clinician-collected samples will be packaged for disposition and transport to the WSLH lab for processing and evaluation. There are no known potential serious risks to the health, safety, or welfare of the subject.

If participants have a primary care provider and did not sign a ROI form at intake and at this time would like their results sent to their provider, a ROI form will be offered to be filled out and signed.

13.1.5 Sample handling and analysis

Clinician-collected samples will be labeled with study ID, participant initials, date of collection and source of collection (cervix) and transported via approved courier to the Wisconsin State Laboratory of Hygiene (WSLH).

Self-collected samples collected using the Evalyn self-collection device will be transferred to a ThinPrep vial for storage and transport. The vial will be labeled with study ID, participant initials, date of collection and source of collection (vaginal self) and transported via approved courier to the Penn State Health Medical Group Laboratory.

13.1.5.1 HPV testing

All samples will be processed at the WSLH (if cervical clinician-collected) or Penn State Health Medical Group Laboratory (if vaginal self-collected) and tested for the presence of 14 oncogenic/high-risk HPV genotypes 16, 18, and other (31,33,35,39,45,51,52,56,58,59,66,68) using the CLIA-certified Roche Cobas4800 HPV Test System (Roche Molecular Systems Inc., Rotkreuz, Switzerland) according to the manufacturer's instructions. Negative samples with the process control (β -globin) DNA concentration that does not fall within Roche's pre-determined range will be considered technically inadequate.

Samples will be pre-aliquoted into properly barcoded 13ml round bottomed sarstedt tubes (2ml) for HPV primary testing according to the Roche Cobas HPV Test package insert. All samples will be run on the Roche Cobas 4800 (for a full HPV workflow following the package insert guidelines). Unsatisfactory results will be run a second time per laboratory standard operating procedure. Results of the sample will be reported to MCHH using standard operating and HIPAA procedures. All HPV Test run results will be analyzed and checked for quality by the Cytology Supervisor.

13.1.5.2 Pap Smear testing

Cytological studies, including cell counts, will be performed on the remaining material in the ThinPrep vials following WSLH standard operating procedure, summarized as follows. Mono-layer smears will be generated on the CLIA-certified Hologic T-5000 platform and stained with Hologic PAP stain using WSLH stain quality controls. Initial screening will be performed by WSLH staff cytotechnologists and quality control screening will be performed by a qualified QC Technologist with five years or more of experience in GYN cytology. Abnormal slides will be reviewed by staff pathologists. Unsatisfactory study samples will be reprocessed at the discretion of the WSLH Cytology Director. All cytology samples will be assessed for 1) adequacy ($>5,000$ cells per slide, estimated based on ten fields counted at 400x magnification) and, 2) diagnoses according to Bethesda System. Clinician-collected cytology cases will be evaluated as part of the routine clinical flow and results reported to MCHH. Cytological results will be grouped as the diagnosis of atypical squamous cells of undetermined significance or higher (ASC-US+) and as high-grade dysplasia (HG cytology). Histological results will be grouped as the diagnosis of cervical intraepithelial neoplasia 2 or higher (CIN2+), cervical intraepithelial neoplasia 3 or higher (CIN3+), and cervical carcinoma (CA).

13.1.5.3 Reporting of results

All results of the samples will be reported to MCHH using standard operating procedures.

For vaginal self-collected samples collected using the Evalyn self-collection device, processed by the Penn State Health Medical Group Laboratory, additional wording will include "This test was developed and its performance characteristics determined by Penn State Health Milton S. Hershey Medical Center laboratory. It has not been cleared or approved by the U.S. Food and Drug Administration. The FDA has determined that such clearance or approval is not necessary. This test is used for clinical purposes. It should not be regarded as investigational or for research. This lab is certified under CLIA-88 as qualified to perform high complexity lab testing. ."

For cervical samples collected by a clinician using the Dacron Brush and stored in ThinPrep vials, CLIA-certified and FDA-approved analysis of the liquid cytology on Hologic T-5000 platform and HPV genotype analysis on the Roche COBAS platform will be used.

13.1.6 Follow-up on results

Samples from screening will be sent via courier to the respective laboratory and results forwarded to MCHH to follow up on results. All participants will be contact by phone regarding their results. Participants with positive results will be asked to return to the community center to discuss the results in-person with MCHH CHWs with a clinician from the study team available virtually to answer any questions. Two attempts will be made to call the participant via phone and if still not reached, a letter will be mailed to the participant's home.

All participants regardless of results will be provided a printed copy of their results via mail or in-person. If a participant does not have a preferred primary care clinic, additional resources will be given on available providers in the area accepting new patients. If participants filled out an ROI form at intake, all results as well as brief letter describing the study will be faxed or mailed to the health care clinic. Guidelines for appropriate follow up by Society for Colposcopy and Cervical Pathology (ASCCP) standards are outlined through an online web application, mobile app, and website (asccp.org/management-guidelines). These management guidelines will be followed for interpreting risk of pathology and recommendation of follow up needs.

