7.2 Telephone Recruitment

The study team will call potential participants using a list of community members who have previously sought services through MCHH. Attempts to reach participants will be two times over a two-week period. All initial discussion with participants from recruitment lists, or when potential subjects contact the study team via other recruitment methods, will include a brief description of the study's purpose, eligibility criteria, and participant involvement will be reviewed. This must also include a statement that participation is voluntary. The screener will ask the caller if she has any questions and whether they are interested in participating. After all questions have been answered, the study team member will ask if the potential subject is interested in proceeding to the next step in recruitment for the study. Potential subjects will answer pre-screening questions using an IRB-approved script. Information collected from potential subjects who fail pre-screening will be destroyed at the end of the study period. Potential subjects who meet all pre-screening criteria will be invited to a particular workshop day in order to go through the consent process.

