9. PROCESS TO DOCUMENT CONSENT IN WRITING

This study requests of waiver of written documentation of consent

- A written script of the information will be provided orally.
- Pre-recorded video of oral script will be available to all participants for future reference.
- Research presents no more than minimal risk of harm to subjects.
- The research involves no procedures for which written consent is normally required outside of the research context.

This consent requests an alteration of the consent process (HRP-410) due to the following criteria:

- The study involves no more than Minimal Risk to the participants based on clinical standard of care.
- The study could not be practically carried out without the alteration. Participants will be blinded to which group they are randomized in order measure participation rates based on which type of screening method they are offered (clinician-collection vs self-collection)
- The alteration will not adversely affect the rights and welfare of the subjects. Participants will be provided the risks of each collection method in detail during the workshops. If a participant declines the type of screening they are offered will then be offered the other screening method.
- Subjects will be provided the additional pertinent information after participation.
- High proportion of participants in this study population have no or low reading or writing literacy in English or the native language.

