13.1.3.1 MCHH Post-Workshop Evaluation Survey (MCHH-PES)

Data collected on the original intake form by MCHH includes the following questions (Figure 3) and will be collected in this study in the same format. Survey will be administered verbally by CHWs in the participants native language. Paper copies of the survey will remain with MCHH and responses copied into Qualtrics survey and continued with questions in the next section (13.2.2. UW Health Researchers Post-Workshop Satisfaction Survey).

Figure 3. MCHH-PES Questions

Participant Evaluation

After today's workshop, how likely are you to...?	Not likely	Neutral	Very Likely	
1. Receive a Pap/Pelvic exam this year or as recommended?	1	2	3	4
2. Spread the word about the screenings available to your family members?	1	2	3	4
3. To encourage your family members to get screened?	1	2	3	4
4. Practice healthy behaviours that can reduce your risks for cervical cancer?	1	2	3	4

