16.3 Confidentiality

There is a slight risk of loss of confidentiality of participant information to subjects enrolled on study. Records will be linked to study ID. Participant identification information will be stored separately and maintained with MCHH for purposes of contacting follow up results. Any information regarding participations will be kept confidential, and to the extent permitted, will not be publicly available. Information collected will be stored on secure, password-protected electronic systems and access will be limited to those involved directly on study.

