23. PROVISIONS TO MONITOR THE DATA TO ENSURE THE SAFETY OF THE PARTICIPANTS

The Principal Investigators (Drs. [name] and [name]) will be responsible for reviewing and monitoring all study data and any adverse events. The Principal Investigator will meet with study personnel at least monthly to evaluate study progress, including periodic assessments of data quality and timeliness, participant recruitment, accrual and retention, participant risk versus benefit, and other factors that can affect study outcomes. All unanticipated problems and adverse events that require reporting to the IRB will be reported to the University of Wisconsin Madison (UW) Health Sciences-IRB (HS-IRB).

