- Location of research activities will be at MCHH's community center with adequate space to conduct workshops activities as well as post-workshop cervical cancer screening.

Availability of medical or psychological resources:

- There will be a medical professional on site for support during and after workshop activities.
- There will be referral to primary care clinicians or other community providers for support of any additional medical or psychological needs as a result of this research study. Anticipated psychological need will be minimal. More than minimal medical need is anticipated for follow-up of abnormal results, this is anticipated and addressed in the protocol.

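### A woman with a positive result who misses two calls is then required to get only written notice, in a population described as having low literacy

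*Combined protocol and SAP*

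**What the plan says.** Section 13.1.6 has every screened woman telephoned with her results. Those with positive results are invited back to discuss them face to face with CHWs, with a clinician available remotely. For a woman who does not answer, the rule is: "Two attempts will be made to call the participant via phone and if still not reached, a letter will be mailed". It does not distinguish positive from negative results, space the calls, or name a step after the letter. The section adds: "All participants regardless of results will be provided a printed copy of their results via mail or in-person".

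Section 9, in justifying the altered consent process, states: "High proportion of participants in this study population have no or low reading or writing literacy in English or the native language". Consent is accordingly given by video and oral script (Sections 8 and 9). For the evaluation survey, Section 13.1.3.1 says: "Survey will be administered verbally by CHWs in the participants native language".

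On follow-up after screening, Section 25 says: "More than minimal medical need is anticipated for follow-up of abnormal results". The same sentence goes on to say that this need is foreseen and dealt with in the protocol, and the bullet refers to onward referral to community clinicians.

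**The concern.** The plan relies on speech for consent and the evaluation survey, and it intends positive results to be discussed in person. For a woman who cannot be raised by telephone, it switches to paper. If she cannot read the letter, the protocol can be followed in full while she stays unaware of a positive screening test. Section 3 says recruitment concentrates on women who are overdue or have never been screened, so many may have no established route by which the result would otherwise reach them. What is at stake is the safety of individual participants, not the validity of the comparison between arms.

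**Working it through.** No calculation applies, and the plan gives no figure to reproduce. The check is whether any part of the plan requires a spoken contact, or a tracked closure, once two calls have failed.

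1. **Section 13.1.6.** Two calls, then a letter. Everyone also gets a printed copy of her results. Both items are written, and they may arrive in one mailing. The letter's language and content are not given.
2. **Section 12.** CHWs telephone with results, and positives are asked to return. The calendar keeps result follow-up running past the last workshop month. Nothing is said about women who are not reached.
3. **Section 18.** Each screened woman is to be contacted and given her results, in person or, if she declines that, by telephone. Results are also mailed to her and, where applicable, to her preferred provider. This states the aim but no action after failed calls.
4. **The clinic route.** Sections 13.1.6 and 14 make the clinic copy depend on an ROI. Section 13.1.4.2 offers the form again at sample collection, but only to women who already have a primary care provider. No section requires the clinic to telephone her.
5. **Section 13.1.1.** Providers taking new patients are briefed, and a cover letter sets out recommended follow-up. This helps only when results are sent to a provider.
6. **Section 14.** Clinician-collected follow-up is described as standard of care, and taking part is said not to hold up care. No mechanism is given for a woman who cannot be reached.
7. **Sections 16.2 and 23.** The REDCap items listed are study ID, workshop date, age, zip code, type of screening and result; none records that a woman received her result. Section 23 says: "The Principal Investigator will meet with study personnel at least monthly to evaluate study progress". It does not name unresolved positives as an item.

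So after the second failed call there is no required spoken step and no required record of closure. Without an ROI, the two written items are all that is owed to her.

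**How many women.** The rule covers screened women in both arms, so the ceiling is 30 workshops × 8 = 240 (Section 11), or 250 by Sections 4 and 20.2. The number with a positive result, two missed calls, no ROI and an unread letter would be far lower. It cannot be estimated, because the documents give no HPV positivity, telephone contact rate, ROI completion rate or literacy percentage for this population.

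**The case against.** The strongest reply is that two calls and a letter is a minimum, and that the surrounding text promises more. Section 18 commits to contacting each screened woman, Section 14 says care will not be delayed, Section 25 says the need is addressed, and Section 23 makes the principal investigators responsible for reviewing all study data. Section 13.1.6 does not forbid a third call, and contact scripts or a contact log may sit in operating procedures outside this document. Harm also needs several things to go wrong together: both calls fail, she cannot read the letter, nobody helps her with it, she does not contact the community organization (MCHH) herself, and no clinic copy prompts anyone to act. The protocol does not treat writing as useless either, since translated handouts accompany the spoken instruction on self-collection.

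Most of this stands, and it limits the weight of the point. What it does not supply is a step after failed calls. Help from a relative is a poor substitute, because it exposes a private result and the intake form lists a spouse's refusal among the barriers to screening.

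Three stronger readings are tempting, and the documents do not support them:

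- A reader might infer that the procedure falls below usual care. The documents give no benchmark for usual care in this situation, and Section 14 asserts the opposite for clinician-collected results.
- A reader might infer that positive results get no more effort than recruitment calls, since Section 7.2 also sets two attempts. That limit governs how often a prospective participant is approached; it is not a standard for notifying results and measures no risk.
- A reader might infer that many positive results will go undelivered. Nothing in the documents allows that count.

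**Conclusion.** The point holds in a narrow form. One rule serves positive and negative results alike, and for a woman with a positive result who misses both calls and has no ROI, the only required notice is one she may be unable to read. This is a weak rule rather than a missing detail: the step is specified, and it fits poorly with what Section 9 says about the population.

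The conclusion assumes that staff do what is written and no more, and that no separate procedure adds calls; the documents neither state nor rule out such a procedure. The number of women affected is unknown and probably small. It is a low-priority improvement to participant safety. The endpoint, sample size and analysis are unaffected.

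**What to change.** In Section 13.1.6, for positive results only:

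- Keep the letter, and require additional CHW calls in the woman's language, with a translator where needed, on different days and at different times. The investigators set the number.
- Limit any voice message to a request to call back that does not reveal the result.
- Record the date on which each positive result was acknowledged.
- Review positives without such a date at the monthly meeting already planned in Section 23.

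The cost is a sentence or two of text, one date per positive result, and a little CHW or translator time. The means exist: the intake form in Appendix A collects telephone number and address, and Section 16.3 says: "Participant identification information will be stored separately and maintained with MCHH for purposes of contacting follow up results". If MCHH already keeps a contact log, the date can go there. The one downside needing care is household privacy, which is why message content is restricted.

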14. COMPARISON OF USUAL CARE AND STUDY PROCEDURES

Standard of care for women recommended by the ASCCP is screening for cervical cancer starting at age 21 with pap smear every three years and then co-testing (HPV and pap smear) starting at age 30. American Cancer Society (ACS) recommends screening starting at age 25 with primarily HPV only every five years. Both societies recommend for screening to continue until age 65 unless history of abnormal results or hysterectomy unrelated to cervical dysplasia.

These research procedures follow standard of care as expected for care delivered to participant population at UW-Madison/UW Health, regarding clinician collection of samples for cervical cancer screening. In both the intervention and control arms of the study, participants will be offered the opportunity for cervical cancer screening via a licensed health care professional. The intervention is education and use of self-collection for HPV only testing using vaginal swab as an additional method to usual care, i.e., pap smear and HPV testing through clinician-collection methods using speculum and cervical swabs (control).

Overall, research has shown self-collection HPV testing as an acceptable method for screening especially in hard-to-reach populations, although concerns remain on potential for false negative results.¹⁵⁻¹⁹ Participants will be informed of this risk and encouraged if opting for self-collection through this method to follow-up with their primary care physician for additional screening per recommended guidelines. Reporting of results will further specify this comparison to standard procedure (outlined in section 13.1.5.3 Reporting of Results).

Otherwise follow up recommendations based on results for clinician-collection (outlined in section 13.1.5 Follow up on Results) is also standard of care, and there will be no delay in care or treatment as a result of being in this study.

If patients have a primary care clinic, their results will not automatically flow into their electronic health record. If an ROI for the PCP has been filled out (see section 13.1.1 and 13.1.3), copy of the results and recommendation for next steps will be provided for continuity of care. Participants will also receive a paper copy of their results to maintain for their own records.

